### 4.4.1 Underlying diseases and medication

Existing underlying diseases (e.g. diabetes, heart failure, obesity, neurological disorders, etc.) can have an impact on incontinence and should be treated appropriately. The influence of obesity as a risk factor for urinary incontinence has been demonstrated [16]. Studies on the therapeutic effect of weight reduction show contradictory results [2].

The influence of medication for comorbidities on urinary incontinence is difficult to assess and the benefit of adapting drug therapies to improve incontinence has not been proven [2].

### 4.4.2 Lifestyle changes

Lifestyle factors that can be associated with incontinence include obesity, smoking, lack of physical activity, drinking habits and diet. Adjusting these factors can improve urinary incontinence [2].

### 4.4.3 Physiotherapy/ pelvic floor training

Pelvic floor exercises are used to improve the function of the pelvic floor and urethral stability.

Meta-analyses have shown that pelvic floor muscle training is effective in terms of curing and relieving urinary incontinence and improving the quality of life of those affected [4] [15] [17] [18]. These effects apply to women with stress incontinence, urge incontinence and mixed urinary incontinence [19].

Improved pelvic floor function can inhibit non-physiological bladder contractions in patients with an overactive bladder, leading to an improvement in symptoms [20]. Pelvic floor training also increases the likelihood of continence 12 months after birth in cases of urinary incontinence caused by pregnancy and childbirth [21]. In addition, older women with stress incontinence benefit from pelvic floor muscle training just as much as younger women [22] [23].

Accordingly, the guidelines recommend carrying out pelvic floor muscle training for both urge and stress incontinence for a period of at least three months [2].

Kranus Health GmbH\_DINKS

#### 4.4.4 Bladder training

Through bladder training, the patient learns to better assess the filling status of the bladder and not to "preventive" emptying of the bladder. Gradually adapted voiding intervals are built up. The specific aims are to correct incorrect habitual patterns, gain control over urge incontinence and ultimately extend the voiding intervals by increasing functional bladder capacity. Incontinence episodes can thus be reduced and patients' self-confidence in their ability to control their bladder function independently is strengthened [2].

#### 4.4.5 Drug therapy

**Antimuscarinic drugs** are a relevant option in the secondary (after failed non-medication therapy) treatment of overactive bladder and urge incontinence. Although the available drugs differ in their pharmacological profiles, what they all have in common is their inhibitory effect on the muscarinic receptors of the detrusor cells. This leads to a reduction in spontaneous, uncoordinated detrusor contractions [2]. The efficacy of antimuscarinic drugs has been proven in numerous studies (overview e.g. in [24]).

Side effects include dry mouth, constipation, accommodation disorders of the eyes, cognitive impairment, tachycardia and fatigue. There is a relatively high discontinuation rate with the main causes being ineffectiveness, side effects and the ability to manage symptoms without medication [2].

The  $\beta$ 3-adrenoreceptor agonist **mirabegron** has also shown efficacy in clinical trials [25]. The side effect profile differs from that of antimuscarinics, whereby the risk of arterial hypertension in particular should be taken into account. However, mirabegron does not lead to any impairment of bladder contractility [2].

**Duloxetine** prevents the presynaptic reuptake of the neurotransmitters serotonin and noradrenaline. This results in increased stimulation of the 5-hydroxytryptamine and noradrenaline receptors on motor pudendal nerves. This leads to increased resting tone and increased contraction force at the striated urethral sphincter [2]. The results from clinical studies are heterogeneous. The German S2 guidelines recommend that women with moderate urinary incontinence and above should be informed about duloxetine as a treatment option [2].

#### 4.4.6 Digital therapy programmes

There are currently no digital health applications for the treatment of female incontinence listed on the BfArM website in Germany (<https://diga.bfarm.de/de/verzeichnis>). However, self-management programmes using smartphones or tablets are listed in the literature. For example, a randomised controlled trial on the effectiveness of an app-based intervention for female urinary incontinence through pelvic floor muscle training, bladder training and knowledge transfer showed after four months that the app therapy was as effective as guideline-based care by general practitioners in the Netherlands [26]. Both treatments led to a relevant reduction in urinary incontinence symptoms, improvement in quality of life and fewer daily incontinence episodes. The authors conclude that app-based therapy is a comparably effective but more accessible alternative to conventional care [26].

Kranus Health GmbH\_DINKS

A systematic review that investigated the intervention of pelvic floor training using an app in women with stress incontinence or stress-related mixed incontinence using six randomised intervention studies found that app-based pelvic floor training significantly reduced the severity of symptoms of stress incontinence in the ICIQ-SF questionnaire and improved the quality of life of the women affected [27]. This demonstrates the effectiveness of app-based pelvic floor exercises for the treatment of stress urinary incontinence and for improving the quality of life of affected women. The results of the Patient Global Impression of Improvement (PGI-I) at follow-up of the studies analysed indicate that participants in the app group experienced a significant improvement [27]. This systematic review focuses on apps that only offer pelvic floor muscle training as an intervention for stress urinary incontinence. A digital health application (DiGA) that integrates other elements of urinary incontinence therapy in addition to pelvic floor muscle training, such as lifestyle changes, fluid management and bladder training - in line with German and European guidelines - could potentially increase effectiveness. A multimodal therapy approach could therefore increase the likelihood of sustainable therapeutic success.

#### 4.5 Conclusions and rationale for the study

Urinary incontinence in women is a very common condition that can be categorised as stress, urge or mixed urinary incontinence. There are various treatment options for different forms of incontinence, including lifestyle changes, physiotherapy/pelvic floor exercises, micturition monitoring and also medication and surgical procedures.

Despite the recommendation in the guidelines [2, 3] and proven effectiveness [4] as a primary therapy, comprehensive, multimodal therapy and monitoring programmes (bladder diary, pelvic floor training, lifestyle changes, fluid management, bladder training, etc.) for female incontinence are rarely offered in clinical practice. The reason for this is the complexity of organisation and implementation in the "analogue" world. Although the treating physician has contact persons (e.g. physiotherapists) available for the individual modules, close and cross-module monitoring of patients, which is essential for the success of treatment [2, 19], cannot be realised in clinical practice. A DiGA can help to close a gap in care by monitoring, treating and alleviating urinary incontinence in line with the areas of application defined in the Digital Healthcare Act.

The positive care effect of such a DiGA is to be demonstrated in a randomised study for patients with stress incontinence (N39.3) and urge incontinence (N39.42) as well as mixed forms. In the intervention arm, patients will have access to a 12-week digital therapy programme based on evidence-based approaches and including measures recommended by German and European guidelines for the treatment of incontinence (see 4.4 Treatment of urinary incontinence). This therapy programme specifically includes pelvic floor training, bladder training, keeping a micturition diary and informative sections on knowledge transfer and education. Previous treatments can be continued in the control arm, i.e. control group patients continue to have access to the reality of care. During the study period, all newly initiated incontinence treatment therapies (e.g. medication, interventional or

Kranus Health GmbH\_DINKS

surgical measures) and categorised as treatment failure. The aim of the study is, among other things, to prove the improvement of disease symptoms, quality of life and patient autonomy.

Kranus Health GmbH\_DINKS

## 5 Study endpoints and supply effects

The aim of this study is to test a multimodal digital therapy via app for women with stress incontinence, urge incontinence and mixed urinary incontinence. The assessment of the positive effects of the treatment is based self-reported documentation by the study patients and validated questionnaires (see appendix).

### 5.1 Incontinence episodes frequency (IEF)

To increase the accuracy of the results, the incontinence episodes are recorded over a period of 72 hours and an average is calculated over 24 hours [12]. This average value per 24 hours is used as the IEF for the assessment of the primary endpoint. The aim is a relative reduction in incontinence episodes (rel-CfB-IEF) of 50% in the app group compared to the control group.

### 5.2 Questionnaires

The standardised assessment of urinary incontinence is carried out using questionnaires validated German (see

**Table 2).** All of the incontinence-specific questionnaires listed below that were selected to record the secondary endpoints of this study are considered Category A questionnaires according to the guidelines and therefore fulfil the criteria for validity, reliability and the recording of changes [2] .

*Table 2: Questionnaires*

Questionnaire	Purpose
ICIQ-SF	Incontinence symptoms
I-QOL	Quality of life
PAM-13	Self-management skills
PGI-I	Overall improvement
S/U-IQ	Distinction between stress and Urge incontinence

#### 5.2.1 ICIQ-SF questionnaire

The International Consultation on Incontinence Questionnaire - Short Form (ICIQ-SF) is a standardised questionnaire to assess urinary incontinence in urology. It was developed to assess the frequency and severity of urinary incontinence and its impact on the quality of life of those affected. The ICIQ-SF comprises four questions, three of which are used to calculate a score with a maximum score of 21 points. The fourth question is asked to determine the urinary leakage situation. Clinically relevant urinary incontinence is defined as four points or more. The German S2 guidelines for urinary incontinence recommend the use of the ICIQ-SF questionnaire to assess the severity of urinary incontinence and to measure changes during the course of interventions. In the study described here, this questionnaire is at the beginning (baseline) and after 12 weeks. This endpoint is

Kranus Health GmbH\_DINKS

is achieved if the change in the ICIQ-SF from baseline to week 12 is > 2.9 points [8, 9].

### 5.2.2 I-QOL questionnaire

The Incontinence Quality-of-Life (I-QOL) is a validated questionnaire recommended by the German guidelines for urinary incontinence, which has been validated for both stress and urge incontinence and assesses the impact of urinary incontinence on quality of life. This questionnaire specialises in assessing the quality of life associated with incontinence problems. The I-QOL questionnaire takes into account emotional, social and physical aspects. Higher scores on the I-QOL indicate a better quality of life, while lower scores indicate greater impairment due to urinary incontinence. There are often specific sub-areas that represent individual aspects of quality of life and scoring can also be done separately for these areas. To assess the change in quality of life, this questionnaire is completed at baseline and after 12 weeks. The endpoint is reached when the change in I-QOL from baseline to week 12 is > 6.3 points [9].

### 5.2.3 PAM-13 Questionnaire

The Patient Activation Measure-13 (PAM-13) is a validated questionnaire designed to measure patients' level of activation in relation to their healthcare. The PAM-13 was developed to assess patients' self-competence and knowledge about their own healthcare. The questionnaire consists of 13 questions that relate to different aspects of patient activation. The questions can cover topics such as understanding of health information, ability to self-organise and willingness to actively participate in their own healthcare. The questionnaire uses a Likert scale anchored between 1 and 4 (1=disagree, 2=somewhat disagree, 3=somewhat agree, 4=strongly agree); the range is from 13 - 52 score points; it is transformed to a scale of 0-100, with higher scores a higher level of activation. Four activation levels are distinguished, reflecting low, basic, moderate and high activation. The PAM-13 enables the assessment of empowerment and the self-management skills of patients. This is completed at the beginning and after 12 weeks.

### 5.2.4 PGI-I questionnaire

The PGI-I questionnaire stands for "Patient Global Impression of Improvement". It is used to record patients' subjective assessment of the improvement in their state of health or symptoms. The questionnaire consists of a single question that asks patients to give their own assessment of the improvement in their state of health. Using the PGI-I questionnaire, patients can rate their health status from "much better" to "much worse". In research and clinical practice, the PGI-I questionnaire is used to take the patient perspective into account when evaluating the effectiveness of interventions. In the study described here, this questionnaire is completed at the end of the study [28].

Kranus Health GmbH\_DINKS

### 5.2.5 S/U-IQ questionnaire

The stress/urge incontinence questionnaire is a validated questionnaire that consists of two questions and makes it possible to differentiate between stress and urge incontinence. In the case of mixed incontinence, this questionnaire helps to determine the dominant incontinence component [29]. It is completed at the beginning and after 12 weeks.

### 5.2.6 Further questions about app use

In week 12, the intervention group receives the following additional questions, which the patient can answer voluntarily:

- Please select the number that best describes the condition of your incontinence now compared to before the therapy: A scale of 1-7 (1 much better - 7 much worse) is provided here.
- How often have you accessed Mictera? (Several times a week, weekly, with longer breaks than 1 week, with longer breaks of between 2-6 weeks, with longer breaks of over 6 weeks, I have not used Mictera)
- If you took longer breaks or did not train with Mictera, what was the reason for this? (free text)
- How are you to recommend Kranus Mictera to others? Answer on a scale of 1-10 (1 Not at all - 10 Very much)
- How satisfied are you with the app? Answer on a scale of 1-10 (1 Not at all - 10 Very much)
- Do you have any comments or suggestions for us? The answer is given here in free text.

The control group is only asked one further question in week 12:

- Do you have any comments for us? This question can be answered in a free text field.

Both groups are asked questions in week 1:

- Please your year of birth.
- Please enter your current weight. (in kg)
- How tall are you? (in cm)

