
Target values/criteria/endpoints:
	
Primary endpoint:
 
(1) Relative change (rel-CfB-IEF) in IEF from baseline to week 12 relative to baseline; desired reduction in mean relative IEF by 50% [6] [7]; IEF per 24 hours - averaged over 72 hours
 
Secondary targets / secondary target criteria:
 
(2) Change (CfB) in the ICIQ-SF from baseline to week 12; expected mean difference between the groups of <math>\geq 2.9</math> points [8, 9]
 
(3) Change in I-QOL from baseline to week 12; expected mean difference between the groups of <math>\geq 6.3</math> points [9]
 
(4) Change in the PAM-13 questionnaire from baseline to week 12
 
(5) PGI-I questionnaire (overall improvement after treatment) at week 12
 
(6) Share of the patients without incontinence (cured patients) at the end of the study
 
(7) Change in micturition frequency per day from baseline to week 12
 
(8) Change in micturition frequency at night from baseline to week 12
 
(9) Change in pad consumption from baseline to week 12
 
(10) Change in imperative urge to urinate from baseline to week 12
 
(11) Change in functional bladder capacity from baseline to week 12
 
(12) Change in body weight from baseline to week 12
 
(13) Proportion of patients with treatment failure within the study period
 
(14) Proportion of patients with at least 50% reduction in IEF from baseline to week 12
 
(15) Change in stress incontinence episodes of the S/U-IQ from baseline to week 12
 
(16) Change in urge incontinence episodes of the S/U-IQ from Baseline at week 12

--	---

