1.5 Business round scheme

Table 1: Visit scheme for the DINKS study

	Study implementation / treatment phase							Follow Up			
	Before enrolment/ pre-screening	Inclusion	Baseline/telephone V1 week 1*	Onboarding IG/ after study inclusion	Technical support call week 2	V2 Week 6*	End of study Telephone V3 week 12*	Onboarding KG/IG	Follow-up questionnaire week 24* (IG, KG)	Follow-up questionnaire week 36* (IG, KG)	Follow-up questionnaire week 48* (IG, KG)
Medical history/basic data collection	X	X									
Stress-Urge-Incontinence-questionnaire (S/U-IQ)			X				X		X	X	X
Verification of input and output Exclusion criteria	X	X									
Clarification, Declaration of consent		X									
Randomisation			X								
Questionnaires (I-QOL and ICIQ-UI-SF)			X				X		X	X	X
PGI-I							X		X	X	X
Technical support				X (IG)	X (IG)			X			
Micturition diary				X (ongoing documentation possible)		X	X	X	X	X	X
Incontinence documentation over 72h		X					X		X	X	X
Acquisition (new) Concomitant medication/therapies	X	X	X			X	X		X	X	X
Recording of adverse events**		X	X	X	X	Additional telephone enquiry	X	X	X	X	X

\*Week +/-7 d

\*\*IA/SAE/Incidentes via SZ, by telephone ([contact]) or by e-mail[[contact]](mailto:[contact]) IG:

Intervention group

KG: Control group

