### 8.3 Secondary endpoints

- 2) Change in ICIQ-SF from baseline to week 12
- 3) Change in I-QOL from baseline to week 12
- 4) Change in the PAM-13 questionnaire from baseline to week 12
- 5) PGI-I questionnaire (overall improvement after treatment) at the end of the study
- 6) Proportion of patients without incontinence (cured patients) at the end of the study
- 7) Reduction in micturition frequency during the day
- 8) Reduction in micturition frequency at night
- 9) Reduction in pad consumption
- 10) Reduction of the imperative urge to urinate
- 11) Change in functional bladder capacity
- 12) Reduction in body weight
- 13) Reduction in the proportion of patients with treatment failure within the study period
- 14) Proportion of patients with at least 50% reduction in IEF from baseline to week 12
- 15) Reduction in the frequency of stress incontinence episodes in the S/U-IQ
- 16) Reduction in the frequency of urge incontinence episodes in the S/U-IQ

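### Secondary endpoint (12), change in body weight to week 12, has no week-12 weight measurement in the data collection that the protocol describes

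*Combined protocol and SAP*

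**What the plan says.** Body weight is a stated secondary objective in the synopsis (section 1.4). There endpoint (12) is "Change in body weight from baseline to week 12". Section 8.3 carries the same endpoint as "12) Reduction in body weight", with no method or time point of its own.

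Section 5.2.6 sets out the questions asked besides the validated instruments:

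- Week 1: "Both groups are asked questions in week 1", and these are year of birth, weight and height. The weight item is "Please enter your current weight. (in kg".
- Week 12, intervention arm: "In week 12, the intervention group receives the following additional questions, which the patient can answer voluntarily". Six items follow: a global rating, frequency of use, reasons for breaks, recommendation, satisfaction and comments.
- Week 12, control arm: "The control group is only asked one further question in week 12". It is a free-text comment.

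Table 1 (section 1.5) has no row for weight. The row "Medical history/basic data collection" is marked only at pre-screening and inclusion. Section 8.8 places endpoint (12) among those reported descriptively with a p-value and a 95% confidence interval.

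**The concern.** A change score needs a value at both ends. The protocol words a weight question at the first time point and none at the second. If the study follows section 5.2.6 as written, a stated objective has no follow-up data in either arm.

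Analysts cannot repair this afterwards. Section 8.8 provides jump-to-reference imputation only for outcomes (1) to (4). If the last-observation-carried-forward sensitivity analysis were applied to endpoint (12) with only baseline weights on file, it would return a change of exactly zero for every woman, which is no information. The likely outcomes are an endpoint that cannot be reported, or one filled from whatever weights happen to exist, with no assurance that the arms were asked alike.

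**Working it through.** The protocol gives no figure to reproduce for this endpoint. The check is a search of each described data source for a weight item and its time point.

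**Required by endpoint (12):** weight at baseline and at week 12, in both arms (section 1.4).

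**Found:**

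| Source | Weight at baseline | Weight at week 12 |
|---|---|---|
| Section 5.2.6, intervention arm | yes (week 1) | no (six other items) |
| Section 5.2.6, control arm | yes (week 1) | no (one comment field) |
| Appendix: PGI-I, I-QOL, ICIQ-SF, PAM-13, S/U-IQ | no item | no item |
| Diary contents, section 6.9.1 | not listed | not listed |
| Table 1 | no weight row | no weight row; basic data not marked |
| Section 8.7 | surveys of weight change named, no item or time point | same |
| Section 8.12 | questionnaires at baseline and end of study, weight not named | same |

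Three further points narrow the possible sources:

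1. Section 9.4 says that only patient-reported measures are collected, so weight has to come from a question put to the woman.
2. Section 3.2 withholds the app from controls for the twelve weeks. Even if the app could hold a weight, it could not supply the comparison.
3. Section 8.11 lists weight with height and age as demographic data, which fits a variable recorded once.

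**Count of described measurements per woman:** baseline 1, week 12 0, in each arm. The change (week 12 minus baseline) therefore has no second term for any participant under the collection as described.

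**Reach.** Secondary endpoints run from (2) to (16), so 16 − 1 = 15. Endpoint (12) is one of these and lies outside the ordered sequence (1) to (4). The case numbers in section 8.4 rest on IEF, ICIQ-SF, I-QOL and PAM-13 and do not involve weight.

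**The case against.** The strongest reply is that the protocol plainly means to collect weight at week 12. Section 8.7 names surveys of weight change, the synopsis fixes the time point, and section 8.12 has electronic questionnaires at both ends. Weight is self-reported, so no centre visit is needed: both arms have a telephone contact and ePRO questionnaires at V3, and either could carry the item. Section 5.2.6 is also not a full inventory of week-12 data, since controls complete the validated questionnaires at that time as well. The list closes only the add-on questions.

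Much of this stands, and it rules out several stronger readings that a reader might infer:

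- **That the endpoint cannot be computed, or that none of the 198 planned women will have a week-12 weight.** The ePRO and eCRF specification is not part of the document. Silence in the protocol is not a forecast of what the database will hold.
- **That no other source can exist because no routine centre visits are planned.** This does not follow for a self-reported value with a V3 contact in place.
- **That the missing row in Table 1 settles the matter.** Table 1 has no PAM-13 row either, although section 5.2.3 schedules PAM-13 at 12 weeks and it is in the ordered tests.
- **That the app would supply weights for the intervention arm only.** No text says that the app records weight.

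What the reply does not do is produce a week-12 item. The baseline weight question is itself one of the add-on questions in section 5.2.6, so its repeat would be expected in the same place, and there the control list is closed by its own wording. Intent without an item or a time point leaves the gap open.

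**Conclusion.** The point holds in a limited form: the protocol promises a change in body weight to week 12 and describes no week-12 weight measurement in either arm. Under the collection as described, the change score is undefined for all participants. This is an inconsistency between the endpoint list and the data-collection text.

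Its size is modest. One descriptive secondary endpoint and its matching objective are affected; the primary endpoint, the ordered tests and the sample size are not. It is still worth correcting, because a measurement missed at week 12 cannot be recovered later.

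The conclusion rests on the protocol text alone and assumes that section 5.2.6 reflects what the ePRO asks. If the ePRO already contains a week-12 weight item for both arms, the fault is one of documentation only.

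**What to change.** Add the existing weight item to the week-12 (V3) questions of both arms in section 5.2.6, with the same wording and the same status in each arm. The intervention-arm list is voluntary, so placing the item there alone would invite unequal response. Add a weight row at V1 and V3 in Table 1. If the ePRO already asks the question, correct section 5.2.6 and Table 1 to match.

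For women already past week 12 without a recorded weight, treat the value as missing. If it was largely not collected, keep endpoint (12) in the report as not assessed and give the reason. Removing it silently would look like selective reporting.

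The cost is one self-report item and a small amendment, with incomplete data if it comes mid-study. The dates show that this is likely. Version 2.1 is dated 14.11.2024, and 84 days earlier is 22.08.2024. Of the 213 days from 01.04.2024 to 31.10.2024, 143 had passed by then. If enrolment had been even over that period, which is an assumption, about 143/213 = 67% of women would have reached week 12 by the date of that version, and an item added then could reach only the remaining third or so.
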